## **1.4. Rationale for Dose Chosen**

### **Apremilast**

Based on the safety and efficacy results of 3 completed Phase 2 studies in psoriasis and PsA, the dose of APR 30 BID was chosen for the BCT-001 study ([Section 1.3](#)), to minimize the number of subjects required to evaluate this rare disorder and to maximize the opportunity to demonstrate efficacy. Since apremilast is known to be associated with gastrointestinal side effects and headaches, the dose was escalated gradually to 30 mg BID over the first week of treatment, and subjects who could not tolerate the full dose of IP were allowed to reduce their dose to 20 mg BID. During the placebo-controlled period, 2 subjects in the APR 30 BID group dose-reduced. During the apremilast-exposure period, 2 subjects in the APR 30 BID/APR 30 BID group dose-reduced; thus although dose reduction was allowed, it was infrequent.

Data from the BCT-001 study indicated that APR 30 BID effectively reduced the number of oral and genital ulcers, decreased oral and genital ulcer pain, and improved physical function and quality of life in subjects with BD. Apremilast exhibited a safety profile in BD that was consistent with those observed in other inflammatory diseases in which apremilast was evaluated (eg, psoriasis and psoriatic arthritis). Taken together, these data demonstrate that APR 30 BID has an acceptable benefit/risk ratio profile in subjects with BD.

Based on this rationale, APR 30 BID will be investigated in this BD study.

## 2. STUDY OBJECTIVES

### 2.1. Primary Objective

- The primary objective of the study is to evaluate the efficacy of apremilast in the treatment of oral ulcers in active Behçet's disease.

### 2.2. Secondary Objectives

The secondary objectives of the study are:

- To evaluate the efficacy of apremilast in subjects with active Behçet's disease
- To evaluate the effect of apremilast on Patient Reported Outcomes (PROs) in subjects with active Behçet's disease

### 2.3. Safety Objective

- To evaluate the safety and tolerability of apremilast in subjects with active Behçet's disease

### 2.4. Exploratory [REDACTED] Objectives

The exploratory [REDACTED] objectives of the study are:

[REDACTED]

### 2.5. Exploratory [REDACTED] Objective

[REDACTED]

### 2.6. Exploratory Objective

The exploratory objective of the study is:

[REDACTED]

Data from exploratory objectives will be included in the Clinical Study Report or a separate report.

### **3. STUDY ENDPOINTS**

#### **3.1. Primary Endpoint**

- Area under the curve (AUC) for the number of oral ulcers from baseline through Week 12

#### **3.2. Secondary Endpoints**

- Complete response rate for oral ulcers at Week 12
  - A complete response is defined as the proportion of subjects who are oral ulcer-free.
- Change from baseline in the pain of oral ulcers as measured by VAS at Week 12
- Complete response rate for genital ulcers at Week 12 for subjects who had genital ulcers at Baseline
  - A complete response is defined as the proportion of subjects who are genital ulcer-free.
- Change from baseline in the pain of genital ulcers, as measured by VAS at Week 12 in subjects who had genital ulcers at baseline
- Change from baseline in disease activity as measured by Behçet's Disease Current Activity scores (BD Current Activity Form) at Week 12
- Change from baseline in the BD QoL score at Week 12
- Change from Baseline in Behçet's Syndrome Activity Score (BSAS) at Week 12
- Time to oral ulcer resolution (complete response), ie, the first instance when a subject has a complete response, during the Placebo-controlled Treatment Phase
- Proportion of subjects with no oral ulcers following complete response, ie, the first time when a subject has a complete response, during the Placebo-controlled Treatment Phase
- Number of oral ulcers following loss of complete response, ie, the first instance when a subject has a reappearance of oral ulcers following a complete response, during the Placebo-controlled Treatment Phase
- Time to recurrence of oral ulcers following loss of complete response, ie, the first instance when a subject has a reappearance of oral ulcers following a complete response, during the Placebo-controlled Treatment Phase
- Change from baseline in the total score of the Static Physician's Global Assessment (PGA) of skin lesions (acne-like lesions, folliculitis and erythema nodosum) of BD at Week 12 in subjects who had BD skin lesions at baseline
- Proportion of subjects achieving an oral ulcer complete response (oral ulcer-free) by Week 6, after start of dosing, and who remain oral ulcer free for at least 6 additional weeks during the 12-week Placebo-controlled Treatment Phase

### 3.3. Safety Endpoints

Safety and tolerability as defined by the following:

- Type, frequency, severity, and relationship of the AEs to apremilast
- Number of subjects who prematurely discontinue IP due to any AE
- Frequency of clinically significant changes in vital signs, and/or laboratory findings

### 3.4. Exploratory [REDACTED] Endpoints

[REDACTED]

### 3.5. Exploratory [REDACTED] Endpoint

[REDACTED]

### 3.6. Exploratory Endpoint(s)

[REDACTED]

## 4. OVERALL STUDY DESIGN

### 4.1. Study Design

This is a Phase 3, multicenter, randomized, double-blind, placebo-controlled, parallel group study, followed by an active-treatment phase to evaluate the efficacy and safety of apremilast (CC-10004) in the treatment of subjects with active BD.

Approximately 204 eligible subjects will be randomized 1:1 (102 subjects per group) to receive apremilast (APR 30 BID) or identically-appearing placebo tablets BID for the 12-week Placebo-controlled Treatment Phase. Subjects will be stratified by gender, history of uveitis and region (Japan and Other).

Upon completion of the Week 12 visit, subjects initially randomized to placebo will transition to APR 30 BID, while subjects initially randomized to APR 30 BID will continue on the same treatment during the 52-week Active Treatment Phase.

Subjects who complete Visit 14 of the 52-week Active Treatment Phase will have an opportunity to continue to receive APR 30 BID in an optional Open-label Extension Phase. Subjects who choose to not enter the optional Open-label Extension Phase will complete the 4-week Posttreatment Observational Follow-up Phase.

Subjects who discontinue at any time from the study for any reason, are to enter the 4-week Posttreatment Observational Follow-up Phase.

The study will include the following (Figure 1):

- Screening Phase: up to 6 weeks
- Double-blind, Placebo-controlled Treatment Phase: 12 weeks
  - APR 30 BID
  - Placebo
- Active Treatment Phase: 52 weeks
  - APR 30 BID
- Optional Open-label Extension Phase until apremilast is commercially available for BD or until the benefit/risk of apremilast is found not to be acceptable for BD, according to either the sponsor or health authority.
  - APR 30 BID
- Posttreatment Observational Follow-up Phase – 4 weeks after the last dose (if a subject early terminates or chooses not to enter the optional Open-label Extension Phase)

#### **4.1.1. Internal Celgene Safety Monitoring During the Apremilast Program: Role of the Safety Management Team**

In addition to daily safety monitoring conducted by Investigators and individual study personnel, cumulative and interval blinded AEs, serious adverse events (SAEs), discontinuations, and laboratory findings are reviewed internally by a Safety Management Team (SMT) at Celgene. The review follows the Council for International Organizations for Medical Sciences, Working Group VI (CIOMS VI) recommendations. The SMT is comprised of lead representatives from multiple Celgene functions engaged in the apremilast development program. The scope, conduct, processes, and accountabilities of the SMT are specified in the SMT charter.

#### **4.1.2. External Safety and Efficacy Monitoring During Apremilast Program: Role of the Independent Data Monitoring Committee**

Monitoring is also performed by an independent, external Data Monitoring Committee (DMC) that will assess both safety and efficacy, as outlined in the DMC charter (available upon request). The DMC will review data in a blinded manner, but reserves the right to unblind data for safety or efficacy reasons. The DMC is comprised of three independent external trialists and an independent external statistician for whom there is no identified conflict of interest. The DMC is convened approximately every 12 months, or ad hoc, at the request of the SMT. The DMC's scope, conduct, processes, and accountabilities are specified in its charter. Recommendations of the DMC, based on the overall benefit/risk evaluation, may include proceeding with the study according to the protocol, proceeding with the study with modification, or study suspension.

### **4.2. Study Design Rationale**

The design of this study was guided by the results from a Phase 2 study in Behçet's disease ([Section 1.3](#)).

The safety profile of apremilast in Behçet's disease was consistent with its known safety profile as demonstrated in the overall development program.

The primary purpose of the CC-10004-BCT-002 study is to evaluate the efficacy of apremilast in the treatment of mucocutaneous manifestations in subjects with Behçet's disease. The primary endpoint will be the AUC for the number of oral ulcers from Day 1 through Week 12. Oral ulcers have spontaneous flares and remissions; thus, using an AUC for the number of oral ulcers from baseline through Week 12 provides a better representation of the effect of apremilast on the number of oral ulcers the subject experiences during the Placebo-controlled Treatment Phase rather than at one point in time, such as Day 85, the primary endpoint, in the CC-10004-BCT-001 study.

#### **Active Treatment Phase**

[figure not shown]
Establishing the long-term safety and tolerability benefit/risk profile of any new therapy, especially one with a new and novel mechanism of action, is a critical aspect of drug development. The 52-week active treatment, wherein all subjects including those initially randomized to placebo receive apremilast, will support the assessment of the long term safety profile of apremilast.

### **Optional Open-label Extension Phase**

Subjects who complete Visit 14 of the 52-week Active Treatment Phase will have an opportunity to continue to receive APR 30 BID in an optional Open-label Extension Phase.

Further to and consistent with the principles of the Declaration of Helsinki, study subjects should also share in any benefit arising from the study, which may include access to treatments identified as being beneficial. For these reasons, a longer active treatment phase and optional Extension Phase, compared to the CC-10004-BCT-001 study, has been included.

**Figure 1: Overall Study Design**

\* Subjects will have an opportunity to enter an Optional Open-label Extension Phase until apremilast is commercially available for BD or until the benefit/risk of apremilast is found not to be acceptable for BD, according to either the sponsor or health authority.

### 4.3. Study Duration

The study will consist of the following phases:

- Screening Phase – up to 6 weeks
- Double-blind, Placebo-controlled Treatment Phase – 12 weeks
- Active Treatment Phase – 52 weeks
- Optional Open-label Extension Phase until apremilast is commercially available for BD or until the benefit/risk of apremilast is found not to be acceptable for BD, according to either the sponsor or health authority.
- Posttreatment Observational Follow-up Phase – 4 weeks after the last dose (if a subject early terminates or chooses not to enter the optional Open-label Extension Phase)

#### **4.4. End of Trial**

The End of Trial is defined as either the date of the last visit of the last subject to complete the study, or the date of receipt of the last data point from the last subject that is required for primary, secondary and/or exploratory analysis, as pre-specified in the protocol and/or the Statistical Analysis Plan, whichever is the later date.

## 5. TABLE OF EVENTS

**Table 1: Table of Events (up to Week 64)**

Phases	Screening Phase	Double-blind, Placebo-controlled Treatment Phase (12 weeks)								Active Treatment Phase (52 weeks)					Post-treatment Observational FU Visit (4 weeks after last dose of IP) a	Early Termination (ET) b	
		2 Randomization	3	4	5	6	7	8	9	10	11	12	13	14			15
Visit Number	1	2	3	4	5	6	7	8	9	10	11	12	13	14	15		
Week	-6 to 0	0	1	2	4	6	8	10	12	16	28	40	52	64	68		
Day	-42 to 0	1	8±1	15±1	29±3	43±3	57±3	71±3	85±3	113±7	197±7	281±7	365±7	449±7	476±7		
Informed Consent	X	-	-	-	-	-	-	-	-	-	-	-	-	-	-	-	
Demography	X	-	-	-	-	-	-	-	-	-	-	-	-	-	-	-	
Medical History including BD history c	X	X	-	-	-	-	-	-	-	-	-	-	-	-	-	-	
Inclusion/Exclusion Criteria	X	X	-	-	-	-	-	-	-	-	-	-	-	-	-	-	
Prior/Concomitant Medications d	X	X	X	X	X	X	X	X	X	X	X	X	X	X	X	X	
Safety Assessments																	
Adverse Events	X	X	X	X	X	X	X	X	X	X	X	X	X	X	X	X	X
Vasculitis and Psychiatric Evaluations e	X	X	X	X	X	X	X	X	X	X	X	X	X	X	X	X	X
Vital Signs f	X	X	X	X	X	X	X	X	X	X	X	X	X	X	X	X	X
Complete Physical Examination g	X	-	-	-	-	-	-	-	X	-	-	-	-	X	-	X	
Limited Physical Examination h	-	X	-	-	X	-	X	-	-	X	X	X	X	-	X	-	
Weight	X	X	X	X	X	X	X	X	X	X	X	X	X	X	X	X	X
Hematology i	X	X	-	-	X	-	-	-	X	X	-	X	X	X	X	X	X
Serum Chemistry j	X	X	-	-	X	-	-	-	X	X	-	X	X	X	X	X	X
Urinalysis k	X	-	-	-	-	-	-	-	-	-	-	-	-	-	-	-	-
Pregnancy Testing l	X	X	-	-	-	-	-	-	X	-	-	-	-	X	X	X	X
Contraception Education m	X	X	X	X	X	X	X	X	X	X	X	X	X	X	X	X	X

**Table 1: Table of Events (Continued)**

Phases	Screening Phase	Double-blind, Placebo-Controlled Treatment Phase (12 weeks)								Active Treatment Phase (52 weeks)					Post-treatment Observational FU Visit (4 weeks after last dose of IP) a)	Early Termination (ET) b)
		2 Randomization	3	4	5	6	7	8	9	10	11	12	13	14		
Visit Number	1	2	3	4	5	6	7	8	9	10	11	12	13	14	15	
Week	-6 to 0	0	1	2	4	6	8	10	12	16	28	40	52	64	68	
Day	-42 to 0	1	8 ±1	15 ±1	29 ±3	43 ±3	57 ±3	71 ±3	85 ±3	113 ±7	197 ±7	281 ±7	365 ±7	449 ±7	476 ±7	
Chest Radiograph n	X	-	-	-	-	-	-	-	-	-	-	-	-	-	-	-
12-lead ECG o	X	-	-	-	-	-	-	-	-	-	-	-	-	-	-	-
Efficacy Assessments																
Number of Oral Ulcers	X	X	X	X	X	X	X	X	X	X	X	X	X	X	X	X
Number of Genital Ulcers	X	X	X	X	X	X	X	X	X	X	X	X	X	X	X	X
Pain VAS for Oral Ulcers	X	X	X	X	X	X	X	X	X	X	X	X	X	X	X	X
Pain VAS for Genital Ulcers	X	X	X	X	X	X	X	X	X	X	X	X	X	X	X	X
BD Current Activity Form	-	X	-	-	-	-	-	-	X	-	-	-	-	X	X	X
BD Quality of Life Measure	-	X	-	-	-	-	-	-	X	-	-	-	-	X	X	X
BSAS	-	X	-	-	-	-	-	-	X	-	-	-	-	X	X	X
Physician's Global Assessment of Skin Lesionsp																
Physician's Global Assessment of Skin Lesions p	-	X	X	X	X	-	X	-	X	X	X	X	X	X	X	X
Assessment of BD-related Inflammatory Eye Diseaser																
Assessment of BD-related Inflammatory Eye Disease r	X	-	-	-	-	-	-	-	X	-	-	-	-	X	-	X

**Table 1: Table of Events (Continued)**

Phases	Screening Phase	Double-blind, Placebo-Controlled Treatment Phase (12 weeks)								Active Treatment Phase (52 weeks)					Post-treatment Observational FU Visit (4 weeks after last dose of IP) a	Early Termination (ET) b
		2 Randomization	3	4	5	6	7	8	9	10	11	12	13	14		
Visit Number	1	2	3	4	5	6	7	8	9	10	11	12	13	14	15	
Week	-6 to 0	0	1	2	4	6	8	10	12	16	28	40	52	64	68	
Day	-42 to 0	1	8 ±1	15 ±1	29 ±3	43 ±3	57 ±3	71 ±3	85 ±3	113 ±7	197 ±7	281 ±7	365 ±7	449 ±7	476 ±7	
Investigational Productw																
Dispense IP	-	X	-	-	X	-	X	-	X	X	X	X	X	X x	-	-
IP Accountability	-	-	X	X	X	-	X	-	X	X	X	X	X	X	-	X

BD = Behçet’s disease; BSAS = Behçet’s Syndrome Activity Score; ECG = electrocardiogram; FU = follow-up; IP = investigational product; ██████████ VAS = visual analog scale.

a Observational Follow-up Visit - Subjects who discontinue at any time from the study for any reason and subjects who do choose to not enter the optional Open-label Extension Phase are to enter the 4-week Posttreatment Observational Follow-up Phase  
b ET assessments are to be completed when a subject withdraws from any of the treatment phases.  
c Medical history and BD-related history (as listed in [Appendix A](#)) will be captured.  
d See [Section 6.5](#) for details.  
e A vasculitis assessment ([Section 6.6.5](#)) and psychiatric evaluation ([Section 6.6.6](#)) are to be assessed as appropriate. Evaluate the need for referral to a psychiatrist and other actions, including discontinuation, as required in [Section 6.6.6](#). Please answer the question in the eCRF as Yes/No for whether the subject was sent for a psychiatric evaluation.  
f Vital signs include temperature, pulse, respiratory rate, and seated blood pressure.  
g Complete physical examinations include height (Visit 1), weight (street clothes; no shoes), skin, nasal cavities, eyes, ears, lymph nodes, genitalia, and respiratory, cardiovascular, gastrointestinal, neurological and musculoskeletal systems evaluations.

- h Limited physical examinations will include evaluations to assess the subject's BD. If a subject presents with symptoms other than BD, the Investigator should determine whether a complete physical examination should be performed.
- i See [Section 6.6.7.1](#) for details.
- j See [Sections 6.6.7.2](#) and [6.6.7.4](#) for details.
- k See [Section 6.6.7.3](#) for details.
- l Urine pregnancy testing (females of childbearing potential [FCBP]) will be performed at Visit 2 (Baseline Visit; prior to randomization). At all other time points indicated in [Section 5](#), a serum pregnancy test will be performed. A urine pregnancy test(s) should be administered if the FCBP subject misses a menstrual period.
- m Contraception education is for males and FCBP. The Investigator will educate all FCBP and males about the different options of contraceptive methods and their correct use at Visits 1 and 2. The subject will be reeducated every time their contraceptive measures/methods or their ability to become pregnant changes.
- n A chest radiograph (posteroanterior [PA] and lateral views) should be taken prior to randomization at Visit 2 (Baseline Visit), when most of the eligibility criteria are met, so that results are available prior to randomization. A PA view is required. An additional lateral view is strongly recommended but not required. Alternatively, PA or PA/lateral radiographs that were taken within the 12 weeks prior to Visit 1 will be accepted. Additional chest radiographs should be performed as indicated by local treatment guidelines or, if guidelines are not available/applicable, chest radiographs should be performed when clinically indicated (see [Section 6.6.10](#)).
- o A 12-lead ECG will be performed after the subject has been supine for 3 minutes. Results must be within normal limits or not clinically significant.
- p See [Appendix G](#) for details.
- q [REDACTED]
- r An ophthalmological exam should be completed during the Screening Phase, once the subject has met most of the eligibility criteria, after the chest radiograph and ECG, but prior to randomization at Visit 2 (Baseline Visit). A complete evaluation of the eyes, including a slit lamp examination, must be performed by an ophthalmologist during the Screening Phase and at Visits 9, 14, ET, and at any time when the subject is suspected of new onset/worsening of Behçet's disease-related inflammatory eye disease, including uveitis, retinitis, ophthalmitis and iritis. If a subject has a report from his/her ophthalmologist, dated within 12 weeks of Visit 2 (Baseline Visit; day of randomization), stating that the subject does not have BD-related ophthalmological symptoms, then the subject will not be required to have an ophthalmological exam during Screening Phase unless there is an eye-related complaint during the Screening Phase.
- s [REDACTED]
- w See [Sections 6.8, 8.3, and 8.6](#) for details.
- x Subjects who complete Visit 14 and choose to continue in the optional Open-label Extension Phase will be dispensed IP at Visit 14.

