### **6.6.9. Pregnancy Tests for Females of Childbearing Potential**

For all FCBP, pregnancy testing will be performed during the study as indicated in Section 5. A serum pregnancy test with a sensitivity of  $\leq 25$  mIU/mL will be required at Visit 1, Visit 9, after the last dose of IP (eg, the ET Visit), and at the Observational Follow-up Visit, (4 weeks after the last dose of IP). In addition, a local urine pregnancy test kit will be provided by the central laboratory and the test performed on all FCBP subjects at Visit 2 (Baseline Visit; day of randomization) at the site, prior to randomization. A urine pregnancy test(s) should be administered if the FCBP subject misses a menstrual period.

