### **6.8.2. Site Instructions for Dosing the Subject**

At each visit that new IP is dispensed, the site staff should make every effort to witness the subject taking the first dose from the new blister card and should record the date and time in the subject's source record

If the subject is seen in the late afternoon or evening, the subject should take the AM tablets at the site, and should skip the PM tablets on that date if it is less than 7 hours before the subject's scheduled bed time. Taking the AM tablets will ensure that subjects who are randomized to an apremilast dose group will receive the active dose from the dose titration card.

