All FCBP must use one of the approved contraceptive options as described below while taking apremilast and for at least 28 days after administration of the last dose of the apremilast.

At the time of study entry, and at any time during the study when a FCBP's contraceptive measures or ability to become pregnant changes, the Investigator will educate the subject regarding contraception options and the correct and consistent use of effective contraceptive methods in order to successfully prevent pregnancy.

All FCBP must have a negative pregnancy test at Visits 1 and 2. All FCBP subjects who engage in activity in which conception is possible must use one of the approved contraceptive options described below:

**Option 1:** Any one of the following highly effective methods: hormonal contraception (oral, injection, implant, transdermal patch, vaginal ring); intrauterine device (IUD); tubal ligation; or partner's vasectomy;

**OR**

**Option 2:** Male or female condom (latex condom or non-latex condom NOT made out of natural [animal] membrane [for example, polyurethane]); PLUS one additional barrier method: (a) diaphragm with spermicide; (b) cervical cap with spermicide; or (c) contraceptive sponge with spermicide.

Male subjects (including those who have had a vasectomy) who engage in activity in which conception is possible must use barrier contraception (latex or non-latex condoms

---

 A female of childbearing potential is a sexually mature female who 1) has not undergone a hysterectomy (the surgical removal of the uterus) or bilateral oophorectomy (the surgical removal of both ovaries) or 2) has not been postmenopausal for at least 24 consecutive months (that is, has had menses at any time during the preceding 24 consecutive months).

NOT made out of natural [animal] membrane [for example, polyurethane]) while on IP and for at least 28 days after the last dose of IP.

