**General Health:**

8. Any significant medical condition, laboratory abnormality, or psychiatric illness that would prevent the subject from participating in the study.
9. Any condition, including the presence of laboratory abnormalities, which places the subject at unacceptable risk if he/she were to participate in the study.
10. Inability to provide voluntary consent.
11. Pregnant women or breast feeding mothers.
12. Systemic or opportunistic fungal infection.
13. Known active current or history of recurrent bacterial, viral, fungal, mycobacterial or other infections (including but not limited to tuberculosis and atypical mycobacterial disease, hepatitis B and C and herpes zoster, histoplasmosis, coccidiomycosis, but excluding onychomycosis) or any major episode of infection requiring hospitalization or treatment with IV or oral antibiotics within 4 weeks of the Screening Phase.
14. Clinically significant abnormality on chest radiograph.
15. Clinically significant abnormality on 12-lead ECG.
16. History of positive test for, or any clinical suspicion of, human immunodeficiency virus (HIV), or congenital or acquired immunodeficiency (eg, common variable immunodeficiency disease).
17. Malignancy or history of malignancy, except for:
- treated (ie, cured) basal cell or squamous cell in situ skin carcinomas;
  - treated (ie, cured) cervical intraepithelial neoplasia (CIN) or carcinoma in situ of the cervix with no evidence of recurrence within the previous 5 years of Visit 1.
18. Any condition that confounds the ability to interpret data from the study.
19. Scheduled surgery or other interventions that would interrupt the subject's participation in the study.
20. Prior history of suicide attempt at any time in the subject's lifetime prior to Visit 2 (Baseline Visit; day of randomization) or major psychiatric illness requiring hospitalization within 3 years prior to Visit 2 (Baseline Visit; day of randomization).

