**Table 5: Treatment Schema for Dose Titration at Visit 9**

	Week 12											
	Day 1		Day 2		Day 3		Day 4		Day 5		Day 6-7	
	AM	PM	AM	PM	AM	PM	AM	PM	AM	PM	AM	PM
APR 30 BID	10mg P 20mg P 30mg A	20mg P 30mg A										
Placebo to APR 30 BID	10mg A 20mg P 30mg P	10mg P 20mg P 30mg P	10mg A 20mg P 30mg P	10mg A 20mg P 30mg P	10mg A 20mg P 30mg P	10mg P 20mg A 30mg P	20mg A 30mg P	20mg A 30mg P	20mg A 30mg P	20mg P 30mg A	20mg P 30mg A	20mg P 30mg A

A=Apremilast; BID= twice daily; P= Placebo.

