### **8.4.2. Active Treatment Phase (52 Weeks)**

All subjects who complete the Placebo-controlled Treatment Phase will be eligible to enter the Active Treatment Phase.

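### Women switching from placebo at Visit 9 can take their first apremilast dose before any current pregnancy result is known; the last required negative is 81 to 87 days old

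*Protocol*

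**What the plan says.** Protocol Section 7.2 makes a negative result a condition of entry: "All FCBP must have a negative pregnancy test at Visits 1 and 2". Exclusion 11 in Section 7.3 is "Pregnant women or breast feeding mothers". Section 6.6.9 places the Visit 2 urine test "at the site, prior to randomization", so the first dose of investigational product (IP) follows a known result.

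Table 1 schedules no pregnancy test at Visits 3 to 8. For scheduled time points other than Visit 2, footnote l states that "a serum pregnancy test will be performed. A urine pregnancy test(s) should be administered if the FCBP subject misses a menstrual period". Section 6.6.9 agrees: the serum test "will be required at Visit 1, Visit 9, after the last dose of IP", and at the follow-up visit.

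Visit 9 is also the switch. Section 8.4.2 sets one condition for going on: "All subjects who complete the Placebo-controlled Treatment Phase will be eligible to enter the Active Treatment Phase". All subjects are given titration cards at that visit (Section 8.3). Section 6.8.2 adds that "the site staff should make every effort to witness the subject taking the first dose from the new blister card". In Table 5, the row "Placebo to APR 30 BID" has an active 10 mg tablet in the Day 1 morning dose. SAP Section 5.2 likewise starts the switchers' apremilast exposure at the Week 12 visit.

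**The concern.** The trial has two points of first exposure to apremilast: Visit 2 for the active arm and Visit 9 for the placebo arm. Only the first is protected by a result that must be known before dosing. At the second, a test is scheduled, but nothing says it must be read before the card is dispensed or the first dose taken. The documents give no turnaround time for the serum test.

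A placebo-arm woman who is pregnant at Visit 9, and whose pregnancy has not been found, can therefore take apremilast before that day's result arrives. Section 6.6.8 describes the risk to a fetus as unknown. Section 11.4.1 stops IP immediately on a positive test or suspected pregnancy, but that rule acts only once there is a result or a suspicion. The issue is one of patient safety and does not touch the efficacy analysis.

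**Working it through.** **Age of the last required negative.** Table 1 puts Visit 2 on Day 1 and Visit 9 on Day 85 ± 3; Week 12 gives 12 × 7 + 1 = 85, which matches.
- Earliest: 82 − 1 = 81 days. Target: 85 − 1 = 84 days. Latest: 88 − 1 = 87 days.

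**Is there an instruction to wait?**
- Visit 2: urine test on site before randomization (footnote l; Section 6.6.9), and a negative is required (Section 7.2).
- Visit 9: serum test (same places). Section 8.4.2 requires only completion of the placebo phase, and Section 8.3 says nothing of a result.
- Elsewhere the protocol writes such ordering out. Section 6.6.10 times the chest radiograph so that its result is in hand at randomization.

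**Number of women.** The documents plan 102 placebo subjects (Section 7.1). The share who are females of childbearing potential (FCBP) is not given; 30-60% is assumed.
- Upper bound, all reaching Visit 9: 102 × 0.3 = 30.6; 102 × 0.6 = 61.2.
- At the Phase 2 completion rate of 100 of 111 (Section 1.3): 102 × 100/111 = 91.9 subjects, giving 27.6 to 55.1 women.

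**Expected conceptions, upper-bound group.** Assumed rate on contraception: 1-5 per 100 woman-years.
- Whole interval: 30.6 × 84/365.25 = 7.04 and 61.2 × 84/365.25 = 14.07 woman-years; × 0.01 and × 0.05 gives 0.070 to 0.704.
- Last 14 days (assumed too recent for a missed period): 1.173 to 2.346 woman-years, giving 0.012 to 0.117.
- Earlier 70 days: 5.864 to 11.729 woman-years, giving 0.059 to 0.586. If 10-30% of these missed periods prompt no test (assumption): 0.006 to 0.176.
- Not yet found at Visit 9: 0.012 + 0.006 = 0.018 to 0.117 + 0.176 = 0.293.
- With 91.9 subjects: 0.011 + 0.005 = 0.016 to 0.106 + 0.159 = 0.264 (components rounded).

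A urine test at Visit 9 would find most of the 0.006 to 0.176 part and few of the last-14-day conceptions.

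**Dose taken before a result.** Active mg for switchers in Table 5, morning/evening: Day 1 10/0, Day 2 10/10, Day 3 10/20. Cumulative: 10, then 10 + 20 = 30, then 30 + 30 = 60 mg. With a same-day result only the 10 mg visit dose is at issue.

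**The case against.** The strongest reply concerns priority, not the text. A Visit 9 test is already scheduled, so only the order of result and dose is open, and IP stops on a positive test. The part of the risk that a urine test could mostly remove is 0.006 to 0.176 pregnancies, roughly one case per 6 to 170 trials of this size (1/0.176 ≈ 6; 1/0.006 ≈ 170). Women are seen at Weeks 1, 2, 4, 6, 8, 10 and 12, which gives repeated chances to notice a missed period. The assumption that 10-30% go untested has no source in the documents.

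The protocol also accepts much longer untested exposure elsewhere. No scheduled test falls between Visit 9 and Visit 14, 52 weeks on drug. With 61 to 122 FCBP over both arms and the same conception rates, that is about 0.6 to 6 conceptions on drug, none of which the proposed test would change. Finally, a dispensing check might sit in the interactive response technology (IRT) requirements document, which is not supplied.

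Most of this stands as a limit on size, and it is why the recommendation rests on low cost and not on frequency. It does not close the gap. The 52-week comparison concerns conceptions during treatment, whereas a pre-dose test addresses a first dose given to a woman already pregnant, which the protocol itself guards against at Visit 2. A check in an unseen document is possible, but nothing in the protocol points to one. The instruction to witness the first dose is a best-effort one, so not every dose need precede the result; the text still permits it.

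**Conclusion.** The gap is real, narrow and cheap to close. The protocol requires no pre-dose pregnancy result at Visit 9, the last required negative is 81 to 87 days old if the visit falls in its window, and the scheduled serum test carries no instruction to wait. It concerns only FCBP switching from placebo, mainly those whose missed period is unreported, unrecognised or irregular, plus some very early conceptions.

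The expected benefit is well below one avoided first exposure in the whole trial. That size rests on three assumptions absent from the documents (FCBP share, conception rate on contraception, share of missed periods untested), and on treating the last 14 days as too recent for a missed period. Confidence is high in the reading of the text and low in the exact magnitude. The change is worth making as a safety improvement.

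**What to change.** Amend footnote l of Table 1 and Section 6.6.9 so that, at Visit 9, every FCBP has the on-site urine test already used at Visit 2, read as negative before IP is dispensed. Apply it in both arms to keep the blind. If positive, withhold the titration card and follow Section 11.4.1. Keep the serum test as confirmation.

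The material cost is one urine kit per FCBP at an existing visit: 204 × 0.3 to 204 × 0.6, about 61 to 122 kits, or 55 to 110 at the Phase 2 completion rate. The larger cost is administrative. Section 14.5 requires written ethics approval before implementation, across about 45 sites (Section 7.1), and Section 14.3 requires re-consent if the consent content changes. The change is therefore best bundled with another amendment. An occasional false positive will delay dispensing, and very early conceptions will still be missed.
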